7.1 Study design

The proposed study is an open-label, exploratory, randomized control trial examining the effect of FSH and rLH (Luveris) versus FSH alone on the number of mature oocytes available for cryopreservation in non-hormone sensitive onco-fertility patients. These patients include those diagnosed with malignancy other than breast, uterine and ovarian cancer.

Given that the care of oncology patients is time sensitive, a random start of the treatment cycle is the usual approach in our clinic, with no prior priming. The patient has a random serum levels of estrogen, progesterone, LH, FSH and HCG levels obtained. A transvaginal ultrasound is performed

as well, and the stage of the cycle is determined. Based on the stage of the cycle, gonadotropin starting time is planned accordingly and the starting dose will be individualized based on AFC as detailed below.

- Early follicular phase: Gonadotropin stimulation started. A GnRH antagonist will be given once the dominant follicle measures >1.4 cm.
- Mid to late follicular phase: patients who have a dominant follicle >1.5 cm with an E2 >300 and a progesterone <5 will be triggered usually with HCG (Ovidrel 250 mcg subcutaneous). After three days gonadotropin stimulation is started.
- Start of luteal phase: start gonadotropin stimulation and once the dominant follicle measure >1.4, a GnRH antagonist will be given.

Patients will be randomly assigned in a 1:1 ratio to either treatment or control group. Treatments in each of the trial arms will be as follows:

- a) Treatment arm: Patients will self-administer a subcutaneous injection of Gonal-F (FSH) in addition to Luveris daily until a pre-set criteria to trigger ovulation is reached.
- b) Control arm: Patients will self-administer a subcutaneous injection of Gonal-F (FSH) alone daily until a pre-set criteria to trigger ovulation is reached.

Transvaginal ultrasound and bloodwork monitoring is initiated to monitor the ovarian response. Once the patient meets one of the following two criteria

- a) A serum estradiol (E2) of greater than 2,000 pmol/L
- b) A follicle measuring greater than 14 mm,

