A daily, subcutaneous injection of a GnRH antagonist (Cetrotide or Ganirelix 0.25 mg) will be administered by the patient subcutaneously to prevent an endogenous surge in LH. Monitoring of the ovarian response will continue until there are 3 or more follicles visualized by transvaginal ultrasound with a mean diameter of ≥17 mm. Ovulation will be subsequently triggered with a subcutaneous injection of HCG or GnRH agonist depending on the managing IVF physician. If a GnRH agonist trigger is chosen, twelve hours after their trigger medication, patients will return to the clinic for blood work including LH and progesterone as per standard procedure. This is a routine confirmatory blood test to confirm that an endogenous LH surge has occurred. In approximately less than 5% of cases, the GnRH agonist trigger fails to elicit an optimal surge, which may require a "rescue" low-dose hCG trigger to be administered 24 hours following the initial trigger. The decision to administer a "rescue" trigger will be at the discretion of the managing IVF physician. Transvaginal, ultrasound-guided oocyte retrieval will be performed approximately 36 hours following the administration of the initial trigger.

Once the oocytes are retrieved, if the patient desires to cryopreserve oocytes, mature oocytes will be cryopreserved by vitrification process. If embryo cryopreservation is planned, the retrieved oocytes will be fertilized in the lab using traditional IVF or ICSI. Embryos will be grown to day 5 and all "good quality" blastocysts will be cryopreserved using vitrification. At our clinic, day 5/6 embryos are considered "good quality" for cryopreservation if they are at least a grade 2BB (or above) on day 5 and/or a 3CC (or above) on day 6, according to the classification system by Gardner and Schoolcraft, 1999 [25].

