7.5 Data collection

The following demographic information will be collected from included patients:

Demographics

- Age
- Gravida/para status
- BMI
- Type of malignancy
- Stage of malignancy (if known)
- Prior history of fertility treatment and the specific type
- Baseline FSH, LH, progesterone, estradiol levels
- Ovarian reserve: AMH and AFC (3-8mm) based on the FORT criteria [22].
- Any history of infertility, categorized as:
 - Anovulation including PCOS
 - o Tubal
 - Male Factor Infertility
 - Endometriosis
 - o Unexplained
 - o Other
 - o None
- Total motile sperm count (if freezing embryos)

Characteristics of treatment cycle

- Type of cycle start (follicular vs. luteal phase)
- Total days of gonadotropin stimulation
- Total dose of FSH (IU)
- Total dose of LH (IU)
- Total number of follicles measuring ≥11 mm on the day of trigger
- Total number of follicles measuring 16-22 mm on the day of trigger, according to FORT criteria [22]
- Type of trigger (hCG vs. GnRH-agonist)
- Need for rescue hCG trigger (ie. failed GnRH agonist trigger)
- Bloodwork on day of trigger ± day after trigger:
 - o E2
 - o LH
 - o Progesterone
- Method of fertilization (standard insemination or ICSI or IVF/ICSI split) if freezing embryos
- Use of a dopamine receptor agonist (Cabergoline) to prevent OHSS

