7.6 Outcome measures

The primary outcome measure will be the total number of mature (MII) oocytes adjusted by antral follicle count (AFC) available for cryopreservation.

Secondary outcome measures will include the following:

- Total number of oocytes retrieved per cycle
- Ratio of mature (MII) to immature oocytes
- Total number of mature oocytes (MII) retrieved per IVF/ICSI cycle
- Oocyte yield (defined as the number of metaphase II (MII) oocytes retrieved divided by the number of follicles ≥15 mm on ultrasound on the day of trigger)
- "Follicular Output Rate" (FORT) (defined as ratio of pre-ovulatory follicles (16-22mm) on day of trigger × 100/AFC (3-8mm) [22]
- Incidence of moderate to critical OHSS based on the classification criteria by Golan et al [26].
- If the embryos are frozen:
 - o Fertilization rate, which will include two outcomes each defined as follows:
 - Definition 1: number of 2PN zygotes divided by the number of mature oocyte(s) fertilized per IVF/ICSI cycle.
 - Definition 2: number of 2PN zygotes divided by the number of oocytes incubated with at least 10,000 sperm per IVF cycle.
 - Total number of good quality day 5 embryos available for cryopreservation determined by an embryologist using the classification system by Gardner and Schoolcraft, 1999 [25].
- Dose-adjusted evaluation of the safety and tolerability of follitropin alfa + lutropin alfa compared to follitropin alfa as measured by incidence of:
 - o Treatment-emergent adverse events (TEAEs)
 - Treatment-related adverse events (AEs)
 - o Incidence of thromboembolic events

8. Study methods

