8.2 Drug formulation, dosage, and reimbursement

The dosing and drug formulations are adherent to the care provided to our cancer patients seeking fertility preservation in our clinic.

Patients will undergo a random start of ovarian stimulation as per the standard of care in our clinic for all onco-fertility patients given that their treatment is time sensitive. Baseline estrogen, progesterone, LH, FSH, HCG levels are measured and a transvaginal ultrasound is performed and the stage of the cycle is determined. Ovarian stimulation will be performed according to results of the transvaginal ultrasound:

- Early follicular phase: FSH and rLH stimulation or FSH alone will be started as per randomization process. A GnRH antagonist will be given once the dominant follicle measures >1.4 cm.
- Mid to late follicular phase: patients who have a dominant follicle >1.5 cm with an E2 >300 and a progesterone <5 will be triggered with human chorionic gonadotropin (hCG, Ovidrel) 250 mcg subcutaneously. After three days, gonadotropin stimulation is started.
- Luteal phase starts: stimulation with FSH and Luveris or FSH alone, and once the dominant follicle measure >1.4 GnRH antagonist will be given.

Dosing:

- Recombinant luteinizing hormone (Luveris): daily dose of 75 IU subcutaneously.
- Follicular stimulating hormone (Gonal-F):
 - o If AFC < 15, FSH dose is 300 units
 - o If AFC > 15, FSH dose is 200 units
- GnRH antagonist dosing: either cetrorelix 250 mcg subcutaneous or ganirelix 250 mcg subcutaneously.
- Trigger of ovulation: Ovidrel 250 mcg or GnRH agonist (Suprefact 0.5 mg).

FSH dosing is based on a retrospective analysis of data from our centre. A multiple regression analysis found only AFC and AMH to be independently associated with higher number of mature oocytes. AMH is unavailable at the start of the treatment cycle as patients require to start chemotherapy immediately. Accordingly, FSH dosing will be based on AFC. Retrospective review of FSH dosing of our centre showed that when the AFC is less than 15, the majority of patients receive an FSH dose of 300 units to maximize the number of oocytes retrieved. When the AFC is equal to or more than 15, the majority of patients receive an FSH dose of 200 units to minimize the risk of ovarian hyperstimulation. FSH dosing in this trial will correspond to this dosing schedule.

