Duration of treatment is guided by measuring serum biochemical markers including estrogen, progesterone, and LH levels. This in addition to monitoring follicular growth by transvaginal ultrasound to assess ovarian response to treatment. By participating in the study, patients will not be subjected to additional investigations or interventions that deviate from the standard of care provided to all our patients undergoing fertility preservation. Patients will not receive compensation for participation in the trial.

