12.2 Planned analysis

The analysis will be performed on an intention-to-treat principle. Continuous variables will be examined for normality using a normal probability plot. Normally distributed continuous variables will be compared using Welch's t-test. Continuous variables not normally distributed will be compared using Mann-Whitney U test. Categorical data will be reported as counts with percentage, and compared with chi-square test or Fisher's exact test whenever appropriate. Additional sensitivity analysis will be performed taking into account potential confounding factors (i.e. Age, AMH, AFC). Regression analysis with age and FSH dose as factors will also be performed. Statistical analysis will be performed using R statistical software (R Foundation for Statistical Computing).

13. Trial registration

The clinical trial will be registered and available online at www.clinicaltrials.gov once the protocol is approved by the Mount Sinai Hospital Research Ethics Board.

14. Knowledge translation

The lack of consensus on the safety and efficacy of rLH in addition to FSH for ovarian stimulation calls for high quality randomized trials. Once the trial is completed and results are available, knowledge translation is of critical importance and involves the translation of findings to policy and practice [30]. Several procedures will be implemented to share the results of this trial internationally given the increasing number of young patients diagnosed with cancer. The study results will be firstly presented at international fertility conferences. The results will also be published in a high impact fertility journal, such as *Human Reproduction*. Experts in the field will be contacted to ensure they are aware of trial results.

15. Role of principal investigator

[name] is a reproductive endocrinologist at Mount Sinai Fertility as well as a Professor in the Department of Obstetrics and Gynecology at Mount Sinai Hospital. She will be supervising all aspects of the trial.

16. References

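### The regression in section 12.2 adjusts for an undefined FSH dose: total dose could bias the rLH effect, and the assigned dose is only a coarse form of AFC

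*Protocol*

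**What the plan says.** Section 12.2 sets an intention-to-treat comparison of the arms by Welch's t-test or Mann-Whitney, with chi-square or Fisher's exact test for categorical data. It then plans a sensitivity analysis that allows for age, AMH and AFC. Last it adds: "Regression analysis with age and FSH dose as factors will also be performed". Neither the outcome of this regression nor the kind of dose is stated.

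Two quantities in the protocol could be the FSH dose:

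- **Assigned dose.** Section 7.1 says that "the starting dose will be individualized based on AFC as detailed below". Section 8.2 gives a two-level rule split at an AFC of 15 (300 or 200 units), the same in both arms, and states: "Accordingly, FSH dosing will be based on AFC".
- **Cumulative dose.** Among the cycle characteristics, section 7.5 has a single FSH dose field (listed as "Total dose of FSH (IU"), next to "Total days of gonadotropin stimulation". It has no field for the starting dose.

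On duration, section 8.2 says: "Duration of treatment is guided by measuring serum biochemical markers including estrogen, progesterone, and LH levels". Section 7.1 says: "Monitoring of the ovarian response will continue until there are 3 or more follicles visualized by transvaginal ultrasound", with a size threshold for those follicles.

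Section 7.6 lists a related secondary outcome: "Dose-adjusted evaluation of the safety and tolerability of follitropin alfa + lutropin alfa compared to follitropin alfa". The drug, the dose measure and the method are not given.

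**The concern.** Randomisation takes place before the cycle starts (section 8.1). Total FSH dose is roughly daily dose times days, and the days depend on hormone levels and follicle growth under treatment. rLH is given to change that response. Total dose is therefore a post-randomisation variable that treatment may affect and that shares causes with oocyte yield, such as ovarian responsiveness. Holding it fixed compares patients who reached the same dose by different routes, and the arm coefficient no longer estimates the effect of assignment. Coasting and cancellation before trigger (section 9.1) add further response-driven influences on total dose, and in an open-label trial those decisions are made with the arm known.

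An adjusted arm effect from this model could then differ from the intention-to-treat result for mechanical reasons. Because the term is undefined, the choice between the two doses could also be made after results are seen.

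The safety item has a similar problem if its adjustment means a regression on total FSH dose or on LH dose.

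**Working it through.** **Plan's own figures.** The protocol gives no number for this regression. The scale comes from section 12.1: control mean 8, SD 4. Its printed formula reproduces: (16 + 16) × (1.96 + 0.84)² / 2² = 62.72, so 63 per group. That formula uses a difference of 2, whereas the stated 20% improvement on 8 is 1.6. This is a separate matter, and both values serve below only as yardsticks.

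**Check 1: closed form for total dose.** Assumed, not in the documents: total-dose SD 600 IU; 250 IU per day (midway between 200 and 300); within-arm correlation ρ between total dose and MII count of -0.2 to -0.6; rLH shifts duration by d days; true effect 1.6.

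Within-arm slope = ρ × 4 / 600 oocytes per IU. Between-arm difference in dose = 250 × d.

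Bias of the arm coefficient = -(ρ × 4 / 600) × (250 × d).

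| ρ | Slope per IU | d = -1: bias, adjusted effect | d = +1: bias, adjusted effect |
|---|---|---|---|
| -0.2 | -0.00133 | -0.33, 1.27 | +0.33, 1.93 |
| -0.4 | -0.00267 | -0.67, 0.93 | +0.67, 2.27 |
| -0.6 | -0.00400 | -1.00, 0.60 | +1.00, 2.60 |

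Simulation with 400,000 patients per scenario gave 1.27, 0.93, 0.59 and 1.93, 2.26, 2.60, which agrees. At d = 0 the bias is 0. At half a day and ρ = -0.2 it is 0.33 / 2 = 0.17, about 10% of 1.6.

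**Check 2: the dose definitions compared.** A second simulation (126 patients, 3,000 runs per scenario) used other assumptions: AFC mean 15, SD 6; starting dose by the section 8.2 rule; 10 days of stimulation; an unmeasured responsiveness that affects both days and yield; a shift of -1, 0 or +1 day; outcome SD about 3.5. Ranges of the mean arm coefficient over scenarios:

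| Adjusted for | True effect 0 | True effect 2 |
|---|---|---|
| Age + starting dose | -0.02 to 0.01 | 1.98 to 2.02 |
| Age + total dose | -0.81 to 0.71 | 1.21 to 2.70 |
| Age + starting + total dose | -1.18 to 1.17 | 0.83 to 3.19 |

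With no shift in duration, none of the models was biased. With total dose alone, the larger errors arose where better responders needed fewer days. Where they stimulated for longer, the error was small (-0.04 and 0.08 at a true effect of 0).

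**Check 3: the safety item.** rLH is 75 IU daily in one arm and absent in the other, so cumulative LH dose = 75 × days in treated patients and 0 in every control. With both arm and LH dose in a model, the arm coefficient becomes an extrapolation to treated patients who received no rLH. That is not the safety contrast of interest. Adjusting for total FSH dose has the problem of Check 1.

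**The case against.** A reader might infer that the protocol definitely adjusts for a quantity set after randomisation. The text does not support that. Section 8.2 uses the term FSH dose for the AFC-assigned amount, section 7.5 adds the word total when it means the cumulative one, and entering dose as a factor suits a two-level variable, though this is not conclusive. No separate field is needed, because the assigned dose follows from AFC, which is collected. On that reading the model is unbiased. What remains is that the term is open to two readings and the only FSH dose field listed points to the harmful one.

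A reader might also take the top of the range, 1.0 oocyte or 63% of a true effect of 1.6, as the expected bias. It is the extreme corner of assumed inputs. Nothing in the protocol shows that rLH changes duration, and nothing shows that it does not. The calculations use MII count, whereas the primary outcome in section 7.6 is adjusted by AFC, so they would need rescaling for a ratio.

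The model is supplementary, in a trial labelled exploratory, and the sentence before it already names age, AMH and AFC. That limits the damage and makes the fix easy, but it does not make a total-dose model valid.

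On safety, the adjustment might mean no more than a tabulation by dose, and an SAP, not available here, may say so. Nor is LH dose strictly collinear with arm, since it varies with days in treated patients. Both points stand, so the safety part is a request for a clear main comparison and not a demonstrated error.

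**Conclusion.** The point holds conditionally. Section 12.2 commits to a covariate that has two meanings in the protocol.

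- **Total dose:** the arm coefficient can be biased in either direction if rLH changes duration. The size rests on inputs outside the documents: zero with no change in duration, and about 0.3 to 1.0 oocytes for a 1-day shift with ρ from -0.2 to -0.6. That is 21% to 63% of a difference of 1.6, or 17% to 50% of 2.
- **Assigned dose:** no bias, provided the AFC rule is followed alike in both arms, but information is lost by cutting AFC at 15.

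Continuous AFC is the better covariate on either reading. It would be wrong to conclude that the primary result is compromised: the intention-to-treat comparison does not condition on dose. The change is worth making but is not critical.

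**What to change.** 1. In section 12.2, replace FSH dose in the regression with continuous baseline AFC. The model then has arm, age stratum (the randomisation stratum) and AFC, with AMH added as a sensitivity analysis. This agrees with the covariates named in the preceding sentence. State the outcome being modelled.
2. Report total FSH dose and days of stimulation by arm as descriptive outcomes. If a model with total dose is kept, label it descriptive and not an estimate of the treatment effect.
3. In section 7.6, make the main safety comparison event incidence by randomised arm, using the categorical tests already planned. Any dose-adjusted tabulation should be descriptive only, because LH dose is zero in all controls and total FSH dose arises after randomisation.

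The cost is wording in two sections. Age, AFC, AMH, total FSH dose and days are already collected, and neither sample size nor treatment changes. What is given up is the dose-adjusted reading of the safety outcome as a formal comparison.
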